## ABBREVIATIONS AND DEFINITIONS OF TERMS

## PROTOCOL SYNOPSIS

Study Title	Wrist Fracture Evaluation with a Desktop Orthopedic Tomosynthesis System
Funder	The University of North Carolina (NC TraCS Institute)
Clinical Phase	Pilot Study
Study Rationale	Tomosynthesis is a quasi-3D imaging modality that uses a series of limited-angle projection images to produce a 3D representation of the object. It provides depth information and removes structural overlaps at significantly reduced radiation dose and cost compared to CT. It is now widely used clinically for breast cancer detection with significantly higher sensitivity and accuracy compared to digital mammography. The value of tomosynthesis for orthopedic imaging has also been demonstrated.
Study Objective(s)	
Primary Objective The primary objective is to compare (using a reader study) the sensitivity of Tomo-E compared to radiography of the wrist in detecting wrist fractures.
 
Secondary Objectives Specificity The secondary aim is to determine the specificity of Tomo-E compared to radiography of the wrist in detecting wrist fractures.
 
Reader Confidence To compare radiologist confidence of Tomo-E compared to wrist radiography for the evaluation of:
 

• Articular surfaces

• Cortical surface of the bones

• Joint spaces

• Soft tissue structures

• Subarticular structures

 
Area Under the Curve (AUC) Comparison To compare the area under the curve (AUC) for Tomo-E compared to wrist radiography for fracture detection.

---

Investigational Device	This study will be an evaluation of a compact extremity tomosynthesis (“Tomo-E”) device to provide 3D imaging at the price and radiation dose of 2D radiography at the point-of-care in orthopedic and radiology clinics. Compared to the current standard practice, 2D radiography, Tomo-E offers increased sensitivity and specificity resulting in better diagnostic accuracy without increasing the radiation dose to the patient or cost to the healthcare system. Successful implementation of the technology will reduce misdiagnosis and overtreatment, and reduce the use of CT scans.
Study Design	This is a prospective, one arm, single center study of 50 that have undergone radiographic imaging of wrist for presumed or known scaphoid, wrist or distal radius fractures to demonstrate Tomo-E’s clinical utility for diagnosis of wrist injury.
Subject Population key criteria for Inclusion and Exclusion:	Inclusion Criteria 

• Age 18 or older

• Undergone radiographic imaging of wrist for presumed or known scaphoid, wrist or distal radius fractures within 2 weeks or are scheduled to undergo such imaging.

• Able to provide informed consent

 Exclusion Criteria 

• Patients with an intervening surgical procedure performed prior to study imaging.

• Institutionalized subject (prisoner or nursing home patient)

Number Of Subjects	A total of 50 participants will be consecutively recruited from individuals that have recently undergone radiographic imaging of wrist for presumed or known scaphoid, wrist or distal radius fractures.
Study Duration	Subjects will be followed for 2 months after initial imaging with the Tomo-E device.
Statistical And Analytic Plan	We will perform sensitivity, specificity and area under the curve (AUC) analysis of the imaging modalities based on radiologist reader studies. We will also perform reader confidence studies in evaluation of imaging characteristics relevant to wrist pain imaging.  The primary outcome of interest is the sensitivity of Tomo-E is defined as the ability of readers (radiologists) to detect wrist

---

fractures in patients. This will be determined by performing a reader study with radiologists. Using these results, we can determine the mean confidence score of radiologist readers using the new device as compared to the competing modality. We will also test the primary null hypothesis that the difference between the two mean confidence scores is zero in the target population.

For the confidence study, the average confidence scores and the corresponding standard deviations will be reported. Furthermore, to test whether the mean confidence score is larger than zero, a linear mixed-effects model will be used to analyze data, where the outcome variable is the confidence scores collected in this study and only a grand mean parameter is in the independent list. Additionally, a random intercept is used in the model to account for the correlation among readers when reading the images from the same patient. The Wald's test based on model fit will be used to test whether the grand mean parameter is larger zero. When the p-value from this test is less than 0.05, it will be concluded that there exists significant evidence that readers have more confidence with the Tomo-E modality compared to the other modality. The estimated mean confidence score is given by the grand mean parameter and its 95% confidence interval will be reported. We anticipate that it would be meaningful to detect a mean confidence score of greater than 1 between the modalities.

---

**DATA AND SAFETY MONITORING PLAN**

[figure not shown]
The Principal Investigator will provide continuous monitoring of patient safety in this trial with periodic reporting to an independent Medical Monitor. The medical monitor will review any reported Unanticipated Adverse Device Effects after patients 5, 25, and 50.

---

## 1. BACKGROUND AND RATIONALE

Trauma to the extremities such wrist, ankle, limb is very common and affects all population groups. It constitutes a significant public health issue. Standard radiography remains the basic imaging tool. However, as a 2-dimensional (2D) imaging modality it lacks sensitivity and specificity. Misdiagnosis rates are known to be high, especially for non-displaced fractures of the scaphoid and talus as well as erosions due to rheumatoid arthritis [1-3]. Misdiagnosis leads to over treatment and unnecessary loss of productivity and quality of life including 6-12 weeks in a cast. Missed fractures can result in a chronic, non-healing fracture that may require surgical fixation and early arthritis of the joint. From a physician perspective, a missed diagnosis can result in a lawsuit and an expensive settlement/penalty.

Computed tomography (CT) offers high resolution and excellent visualization of bone and joint morphology, and Magnetic Resonance Imaging (MRI) delivers soft tissue and cartilage visibility. However, cost, space and workflow related issues make them prohibitive for small orthopedic clinics. Although the radiation dose of a CT scan has been reduced considerably in recent years, it is still significantly higher than a regular radiograph. The whole-body scanners also have difficulties in imaging patients in portable and weight-bearing conditions. Dedicated extremity CT scanners (Figure 1) have been commercialized recently in an attempt to address the current deficiency. They still suffer from higher cost and at such have a limited installation base.

[figure not shown]
## 1.1 Introduction

Tomosynthesis is a quasi-3D imaging modality that uses a series of limited-angle projection images to produce a 3D representation of the object [4]. It provides depth information and removes structural overlaps at significantly reduced radiation dose and cost compared to CT. It is now widely used clinically for breast cancer detection with significantly higher sensitivity and accuracy compared to digital mammography. The value of tomosynthesis for orthopedic imaging has also been demonstrated [1, 2, 5].

## 1.2 Extremity Tomosynthesis

This study will be an evaluation of a compact extremity tomosynthesis (“Tomo-E”) device to provide 3D imaging at the price and radiation dose of 2D radiography at the point-of-care in orthopedic and radiology clinics. Compared to the current standard practice, 2D radiography, Tomo-E offers increased sensitivity and specificity resulting in better diagnostic accuracy without increasing the radiation dose to the patient or cost to the healthcare system. Successful implementation of the technology will reduce misdiagnosis and overtreatment, and reduce the use of CT scans. The device is enabled by the unique UNC-invented carbon nanotube (CNT) x-ray source array [6] and stationary tomosynthesis technologies [7].

This will be carried out using an existing and re-configurable imaging set-up (Figure 4), and an iterative image reconstruction algorithm developed in-house, which has been utilized in our preliminary studies using cadaveric hands. The device will be modified to meet the safety standards for patient imaging and will be characterized and tested.

this study (right). Bottom: Reconstructed tomosynthesis images of a hand phantom at different depth. The images were collected using the experimental set-up shown above

The research images will not be interpreted or analyzed for clinical decisions related to the patient. As such, this study will request that the IRB make a determination that this study is no greater than minimal risk. This study meets all the requirements for an NSR determination including:

- The device will not be implanted.
- The device is not intended to support or sustain human life.
- The device is not being used of substantial importance in diagnosing, curing, mitigating, or treating disease.
- The device does not present a potential for serious risk to health, safety, or welfare of a subject.

### 1.3 Non-Clinical and Clinical Study Findings

Two dimensional radiography is the most commonly used diagnostic tool for orthopedic examinations. Although its low accuracy is well known, it remains the most cost effective screening tool. Tomosynthesis is gaining clinical acceptance as a low-dose modality that increases diagnostic sensitivity compared to 2D radiography while using significantly lower radiation dose compared to 3D.

Current commercial approaches: Commercial tomosynthesis scanners collect the projection images needed for reconstruction by mechanically moving a large single-beam x-ray tube mounted on a motorized arm across a long distance while taking the x-ray exposures (Figure 1). Because of the tube motion blurring its spatial sensitivity and consequently the detection sensitivity are lower than what the modality can intrinsically provide (Figure 1). Furthermore, the device is expensive (~\$150K), and requires a dedicated imaging room. The technology has not made a significant inroad to orthopedic clinics.

Our innovation: Tomo-E is a compact and stationary device that utilizes a distributed CNT x-ray source array that will be specially designed for extremity imaging to collect all the projection views without any mechanical motion, as illustrated in **Figure 2**. X-ray exposure is synchronized with a high frame-rate x-ray detector, which is controlled via dedicated control electronics. The entire device is packaged in radiation shielding and will be operated at the point-of-care (Figure 3). The projection images are processed by a fast iterative tomosynthesis reconstruction algorithm developed at UNC. The reconstructed images are generated in the DICOM format and can be viewed in standard clinical PACS systems. Imaging can be performed with the patient either

sitting in the examination chair or with the patient standing in the load-bearing situation (Figure 3).

Figure 3: Photos illustrating the proposed compact Tomo-E device for quasi-3D extremity imaging (The photo on the right is a commercial 2D radiography machine. Tomo-E is expected to have a similar dimension)

Compared to 2D radiography this quasi-3D method offers higher diagnostic accuracy to allow physicians to make better treatment decisions, prevent unnecessary patient casting, and reduces the use high-dose/cost MRI or CT imaging. Compared to commercial tomosynthesis systems, Tomo-E will be the world's first compact 3D orthopedic imaging system that can be used as point-of-care, is low cost, and offers higher spatial resolution.

Figure 4: Left: a FDA approved CNT x-ray based digital mobile x-ray radiography system on display at RSAN 2017. Right: a schematic showing a CNT x-ray source array

Preliminary studies using phantoms and cadaveric tissue have been performed to optimize the system configuration for orthopedic imaging. **Figure 2** shows an example of the reconstructed tomosynthesis images of a cadaveric hand obtained from this

device. Utilizing a set of 25 cadaveric hands ([name], MD), we have established the geometry, dose parameters and image resolution necessary to provide diagnostic quality wrist radiographs through a reader study with musculoskeletal radiologists.

## **2. STUDY OBJECTIVES**

The aim of this one-year study is to demonstrate Tomo-E's clinical utility for diagnosis of wrist fractures.

### **2.1 Primary Objective**

The primary objective is to compare (using a reader study) the sensitivity of Tomo-E compared to radiography of the wrist in detecting wrist fractures.

### **2.2 Secondary Objectives**

#### **2.2.1 Specificity**

The secondary aim is to determine the specificity of Tomo-E compared to radiography of the wrist in detecting wrist fractures.

#### **2.2.2 Reader Confidence**

To compare radiologist confidence of Tomo-E compared to wrist radiography for the evaluation of:

- Articular surfaces
- Cortical surface of the bones
- Joint spaces
- Soft tissue structures
- Subarticular structures

#### **2.2.3 Area Under the Curve (AUC) Comparison**

To compare the area under the curve (AUC) for Tomo-E compared to wrist radiography for fracture detection.

## **3. INVESTIGATIONAL PLAN**

### **3.1 Study Design**

This is a prospective, one arm, single center study of 50 that have undergone radiographic imaging of wrist for presumed or known scaphoid, wrist or distal radius fractures to demonstrate Tomo-E's clinical utility for diagnosis of wrist injury.

### **3.2 Study Duration, Enrollment and Number of Subjects**

We will include a total of 50 participants in this trial. These subjects will be followed for 2 months after initial imaging with the Tomo-E device.

### **3.3 Study Population**

#### **3.3.1 Inclusion Criteria**

##### **3.3.1.1 Age 18 or older**

**3.3.1.2** Undergone radiographic imaging of wrist for presumed or known scaphoid, wrist or distal radius fractures within 2 weeks or are scheduled to undergo such imaging.

**3.3.1.3** Able to provide informed consent

### **3.3.2 Exclusion Criteria**

**3.3.2.1** Patients with an intervening surgical procedure performed prior to study imaging.

**3.3.2.2** Institutionalized subject (prisoner or nursing home patient)

## **4. STUDY PROCEDURES**

A patient study focusing on wrist injury will be carried out by comparing Tomo-E with conventional 2D radiographs obtained from a clinical device at UNC Radiology or Orthopedic clinics. Fifty patients who have wrist injuries and have been imaged by conventional 2D radiography at UNC orthopedic clinic (at the Ambulatory Care Center) or Urgent Care will be recruited and be imaged using the Tomo-E device which will be installed in our clinical imaging space in the Marsico Hall, located approximately 200 yards away. We will recruit subjects ages 18 and above to evaluate the device in the adult population. The images will be compared and evaluated by 3 experienced musculoskeletal radiologists from UNC. Clinical outcome reviewed up to 2 months after initial imaging will serve as the clinical standard for the presence of fracture.

### **4.1 Screening/Baseline Visit procedures**

A total of 50 participants will be enrolled to this study. The 50 study subjects will be consecutively recruited from individuals that have recently undergone radiographic imaging of wrist for presumed or known scaphoid, wrist or distal radius fractures.

Eligible patients will be identified by research staff review in coordination with the UNC Radiology Clinic.

Once a patient has been referred, the patient will be approached by a coordinator from Radiology to assess interest in participation.

All eligible participants who agree to participate in the study will be asked to come to their scheduled appointment thirty minutes early to complete the informed consent process. For patients who have already undergone their clinical imaging, they will be scheduled to return to UNC for the study visit.

Review of the consent will take place in the privacy of an exam room, or when possible, a sample consent form will be sent to the patient via email prior to the patient's visit to allow for ample review.

### **4.2 Research Imaging Procedure**

Participants who consent for the study will be escorted by the research coordinator to the dedicated study room for the imaging exam.

The patient will have the Tomo-E scan performed in a similar manner as conventional wrist radiography. The research technologist will assist in positioning the wrist in the tomosynthesis unit. Once positioned, the total scan time is approximately 15 seconds. The length of time for the positioning and examination of a subject's wrist may vary but it is expected that the entire imaging procedure will take about 5-10 min, including positioning time.

#### **4.3 Medical Record Abstraction**

Participants' medical record will be reviewed for 2 months following their initial research imaging to meet the primary and secondary aims.

#### **4.4 Reader Study**

Upon completion of all study image data collection, a reader study will be performed with three MSK fellowship trained radiologists. All images will be reconstructed with our fast-reconstruction algorithm and presented on 3MP viewing monitors with PACS viewing software with conventional zoom/pan/window and level tools. The readers will not be blinded whether the images are from Tomo-E.

Each radiologist will be randomly presented with either the patient's diagnostic radiographs or tomosynthesis study in a random order. They will be asked to review the scan for the presence of a fracture, and comment on location (specific bone) and fracture type. They will be asked their confidence rating on a scale of 0 to 100%.

A washout period of four weeks will be utilized so that the radiologists will have "forgotten" their initial interpretations. At this timepoint, the other modality for each patient will be randomly presented. Diagnostic accuracy will be defined by the presence of a fracture as defined by the clinical diagnosis by the attending orthopedic surgeon at 2 months post imaging during the patients' routine clinical care, such as cast placement, surgery, or follow-up imaging. Sensitivity and specificity to the presence of fractures will be estimated and evaluated between the modalities.

The order that imaging modalities will be presented will be randomly assigned using a computational software in collaboration with the study biostatistician. This randomization schedule will be created prior to the beginning of the reader study and will not be shared with any of the readers.

#### **4.5 Variables of Interest**

Primary Variables of Interest:

- Presence of fracture based on imaging (T/F)
- Confidence in interpretation of image set (0 to 100%)

Secondary Variables of Interest

- Reader confidence in articular surface evaluation (1-5)
- Reader confidence in Cortical surface evaluation (1-5)
- Reader confidence in Joint Space evaluation (1-5)

- Reader confidence in Soft tissue Structures evaluation (1-5)
- Reader confidence in Subarticular structure evaluation (1-5)

## 5. STATISTICAL CONSIDERATION

### 5.1 Primary Endpoint

The sensitivity of Tomo-E is defined as the ability of readers (radiologists) to detect wrist fractures in patients. Diagnostic accuracy will be defined by the presence of a fracture as defined clinically by the attending orthopedic surgeon at 2 months post imaging.

### 5.2 Secondary Endpoint

The specificity of Tomo-E is defined as the ability to distinguish between individuals that do not have a wrist fracture. Diagnostic accuracy will be defined by the presence of a fracture as defined clinically by the attending orthopedic surgeon at 2 months post imaging.

### 5.3 Statistical Methods

A total of 50 participants will be recruited for this study. Three radiologists will be recruited to conduct the reader study.

We will perform sensitivity, specificity and area under the curve (AUC) analysis of the imaging modalities based on radiologist reader studies. We will also perform reader confidence studies in evaluation of imaging characteristics relevant to wrist pain imaging.

The primary outcome of interest is the sensitivity of Tomo-E is defined as the ability of readers (radiologists) to detect wrist fractures in patients. This will be determined by performing a reader study with radiologists. Using these results, we can determine the mean confidence score of radiologist readers using the new device as compared to the competing modality. We will also test the primary null hypothesis that the difference between the two mean confidence scores is zero in the target population.

For the confidence study, the average confidence scores and the corresponding standard deviations will be reported. Furthermore, to test whether the mean confidence score is larger than zero, a linear mixed-effects model will be used to analyze data, where the outcome variable is the confidence scores collected in this study and only a grand mean parameter is in the independent list. Additionally, a random intercept is used in the model to account for the correlation among readers when reading the images from the same patient. The Wald's test based on model fit will be used to test whether the grand mean parameter is larger zero. When the p-value from this test is less than 0.05, it will be concluded that there exists significant evidence that readers have more confidence with the Tomo-E modality compared to the other modality. The estimated mean confidence score is given by the grand mean parameter and its 95% confidence interval will be reported. We anticipate that it would be meaningful to detect a mean confidence score of greater than 1 between the modalities.

For the primary and secondary objective, we will estimate the sensitivity and specificity for a pre-specified cutoff of review scores to detect wrist fracture. Generalized estimating equation will be used to produce such estimates, where diagnosis outcomes from readers are treated as clustered data and a compound symmetry working covariance matrix is used. Normal distributions will be used to construct 95% confidence intervals. Bootstrap method may be used when the normality assumption is of concern. For the AUC analysis, the same estimating procedures will be used to obtain the sensitivity and specificity when varying cutoff scores then the AUC will be calculated using the trapezoidal rule. The confidence of the AUC will be obtained from bootstrap method.

For the confidence study, we expect no missing data or drop out. For any missed data during the reader study, we will question the reader to collect the data. The only primary hypothesis test is whether the mean confidence score is zero with a significance level of 0.05. There is no need to adjust multiple tests. All hypothesis tests that are observed to be not statistically significant will be reported as being inconclusive.

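### Section 5.3 sets a zero-difference null for reader confidence, but the model as written tests whether the raw ratings average above zero

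*Combined protocol and SAP*

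**What the plan says.** The third paragraph of section 5.3, repeated in the synopsis, says the trial will "test the primary null hypothesis that the difference between the two mean confidence scores is zero in the target population". The next paragraph gives the model. It is a linear mixed model in which "the outcome variable is the confidence scores collected in this study and only a grand mean parameter is in the independent list", with a random intercept for patient. A Wald test asks whether the grand mean is above zero. If p is below 0.05, "it will be concluded that there exists significant evidence that readers have more confidence with the Tomo-E modality compared to the other modality". The paragraph closes by saying that "it would be meaningful to detect a mean confidence score of greater than 1 between the modalities".

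The last paragraph of 5.3 restates the test without mentioning a difference: "The only primary hypothesis test is whether the mean confidence score is zero with a significance level of 0.05".

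The ratings are described elsewhere:

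- **Section 4.4.** Each reader reads one modality per patient and, after a four-week washout, the other. On the rating itself: "They will be asked their confidence rating on a scale of 0 to 100" percent.
- **Section 4.5.** A 0-100 confidence in interpreting the image set is a primary variable, and five 1-5 feature ratings are secondary.
- **Appendix A.** The form collects a 0-100 confidence that a fracture is present, and five graded items. It has no comparative item.

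**The concern.** The hypothesis concerns a contrast between modalities, but the model contains no contrast. The outcome sentence points to the ratings as collected, each belonging to a single modality. The only fixed effect is an overall mean, and nothing in the model distinguishes a Tomo-E read from a radiograph read. A mean of ratings that cannot be negative will lie above zero whatever the device does, yet the decision rule turns that result into a claim for Tomo-E.

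This matters because 5.3 calls it the only primary hypothesis test. Followed to the letter, the plan would declare greater confidence with Tomo-E even if Tomo-E reduced it.

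**Working it through.** The documents give no power, SD or expected mean for the confidence test, so there is no figure of the plan's to reproduce. The 70% power in section 5.4 concerns sensitivity.

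**Inputs from the documents:** 50 patients, 3 readers and 2 modalities, so 6 scores per patient and 300 in all; scales 0-100 and 1-5; prevalence 33%; sensitivity 65% (radiography) and 80% (Tomo-E).

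**1. Bound on the 0-100 score, needing no SD.** With balanced data the estimated grand mean is the overall mean m. Its standard error is the population SD of the 50 patient means divided by √49 = 7. Patient means lie between 0 and 100, so their variance is at most m(100 − m). Hence

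z ≥ 7 × √(m / (100 − m)).

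- z = 1.645: m/(100 − m) = (1.645/7)² = 0.0552, so m = 5.2.
- z = 1.96: m/(100 − m) = (1.96/7)² = 0.0784, so m = 7.3.

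If the patient variance is estimated as zero, the factor 7 becomes √299 and the bound is higher still.

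**2. Bound on the 1-5 items.** The smallest z arises with 8 of 50 patients rated 5 throughout and the rest rated 1. The mean is 1 + 4 × 0.16 = 1.64, the SD is 4 × √(0.16 × 0.84) = 1.466, and z = 7 × 1.64/1.466 = 7.8. Rejection is certain.

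**3. Could the 0-100 mean be low enough to escape?** The form's wording is the least favourable case, because a confident negative read scores low. Assume no false positives and every negative read scored 0. With the 5.4 figures the share of positive reads is 0.33 × (0.65 + 0.80)/2 = 0.239. If positive reads average c, the expected mean is 0.239c, which passes 7.27 at c = 30.4. At c = 50 (assumed) the mean is 12.0 and z ≥ 7 × √(12.0/88.0) = 2.58.

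**4. Simulation, 20,000 trials per case.** SDs, scores per read and reader correlations are assumptions.

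| Case | Raw-score test rejects | Paired-difference test |
|---|---|---|
| Interpretation wording, no difference (four SD sets, means 30 to 70) | 100% | about 5% one-sided, 5-6% two-sided |
| Interpretation wording, Tomo-E 10 points lower | 100% | one-sided claim for Tomo-E in about 0% |
| Form wording, 65% sensitivity for both, positive reads scored 50 | 99.8-100% | about 1-4% |
| Form wording, Tomo-E positive reads 50 against 70 | 99.8-100% | one-sided claim in about 0.01% or fewer |
| Form wording, Tomo-E sensitivity 50% against 65% | 99.7-100% | one-sided claim in at most 0.05% |

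Form-wording ranges run over latent reader correlations of 0.3, 0.7 and 0.95. As an example of scale, take interpretation wording with mean 70, patient SD 10, and per-modality patient and residual SDs of 5.7 and 10.6. The raw-score z then averages about 44 with no difference and 41 with Tomo-E 10 points lower.

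**5. Direction.** On paired differences with Tomo-E 10 points lower, a two-sided test at 1.96 rejects in roughly 60 to 100% of trials, depending on the SDs. Read two-sided, the p < 0.05 rule would turn those results into claims for Tomo-E unless a positive estimate is also required.

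**6. Scale of the threshold.** A difference of 1 is 1/100 of the range on the 0-100 score and 1/4 of the range on a 1-5 item.

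**The case against.** The strongest reply is that 5.3 largely explains itself. It frames the score as a comparison with the competing modality, states a zero-difference null, reads a positive grand mean as favouring Tomo-E, and puts the meaningful value between the modalities. These fit together only if the score is a paired difference, and for a paired difference an intercept-only model is sound. A statistician coding the raw-score version would probably notice that it is empty. Most of this stands. What remains is that the sentence defining the outcome names something else, and the last paragraph of 5.3 repeats the slip, so the rule as written is wrong.

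Three stronger readings are tempting, and the documents do not support them:

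- **The method is unworkable.** It is not. With the outcome defined as a difference, its error rate is close to nominal for these readers.
- **Sidedness is nowhere stated.** Section 5.3 twice gives a direction, above zero. The restatement as a test of equality to zero may simply be the null. The two need aligning.
- **The accuracy results are compromised.** Sensitivity and specificity are estimated separately by generalized estimating equations and do not use this model.

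A fair limit on the remedy is that a patient random intercept alone supports inference for these three readers only. With difference-score SDs of 8 (patient) and 15 (residual), adding reader-by-modality SDs of 2 or 5 points (assumed) raises two-sided rejection to about 11% or 33%, if the target is a zero mean difference across a wider population of readers.

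**Conclusion.** The point holds as an error in the written rule. The model in 5.3 and its copy in the synopsis does not test the null stated beside it. That it must reject once the overall 0-100 mean passes 7.3 rests only on 50 patients, complete data and the scale. The 99.7 to 100% rejection rates rest on assumed SDs, scores and reader correlations.

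The intended analysis was very probably a paired difference, with about 5 to 6% type I error for these three readers (about 1 to 4% on sparse form-wording data) and no claim to a wider reader population. The plan should be corrected because this is its only primary hypothesis test. The point is not graver than that: the primary objective and endpoint are sensitivity (2.1, 5.1), reader confidence is a secondary objective (2.2.2), and the sensitivity and specificity estimates do not change.

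**What to change.** In 5.3 and the synopsis, choose one of two forms:

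- Define the outcome as the within-patient, within-reader difference, Tomo-E minus radiograph, and keep the intercept-only model with a patient random intercept.
- Model the raw scores with a modality fixed effect plus patient and patient-by-modality random effects, and test the modality coefficient.

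Then reword the last paragraph of 5.3 so that the hypothesis is a zero mean difference. Align the directional and non-directional wording, and claim more confidence with Tomo-E only when the estimate is positive. State that the inference is for these three readers.

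Three clarifications belong with this change. Name the tested score in 5.3, presumably the 0-100 score that 4.5 lists as primary. Reconcile its meaning between 4.5 (confidence in interpreting the image set) and Appendix A (confidence that a fracture is present), since a confident negative read scores high on one and low on the other, and subtracting modalities does not cure that. Give the scale for the threshold of 1.

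The cost is one paragraph and its synopsis copy, one further sentence in 5.3, and one line of wording in 4.5 or on the form. No new patients or images are needed. The meaning of the score must be settled before the reads begin, because ratings collected under the wrong meaning cannot be repaired afterwards.
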